STUDY PROPOSAL

**Intraoperative Ketamine and Methadone for
Laminectomy: Effect on Recovery, Postoperative Pain,
and Opioid Requirements**

IRB #: Pro00030109

NCT02252432

Date: 02/15/2020

**Intraoperative Ketamine and Methadone for Laminectomy: Effect on Recovery,
Postoperative Pain, and Opioid Requirements**

IRB #: Pro00030109

PRINCIPAL INVESTIGATOR

[name]., Ph.D.

CO-INVESTIGATORS

[name] [name].

INSTITUTION

Department of Anesthesiology
Cedars-Sinai Medical Center
[name]
[name]

E-MAIL

[contact]

[contact]

[contact]

STUDY OBJECTIVES

1. To determine if intraoperative double NMDA antagonism with ketamine + methadone reduces postoperative pain scores and opioid consumption more than single NMDA antagonism with ketamine or methadone alone after lumbar laminectomy.
2. To compare the side effects and hospital course between post-laminectomy patients receiving intraoperative ketamine + methadone vs. ketamine or methadone alone.

BACKGROUND & SIGNIFICANCE

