Patients given methadone during anesthetic induction demonstrated a 50% reduction in opiate requirements and VAS pain scores at 48h post spine surgery, but not at 24 hours (11). Several prospective, randomized controlled studies have found that methadone was superior to morphine in duration of postoperative pain relief and opioid requirements. The methadone group averaged 20.7 hours of sustained post-surgical pain relief compared to 6 hours with morphine and required significantly less quantities (11.5 ± 8.5 mg vs. 41 ± 14.1 mg) (11). Similar studies have confirmed methadone's benefits (12, 13). Thus, ketamine may have maximum benefit in controlling postoperative pain and decreasing opioid-induced side effects the initial 24 hours while methadone can continue to provide pain relief for up to 48 hours. The use of methadone in perioperative pain management is frequently employed by anesthesiologists caring for patients undergoing spine surgery at our institution and is within the standard of care.

Although it is clear that ketamine and methadone both provide significant post-op pain relief and opiate-sparing effects for chronic pain patients, their combined effects remain largely unknown. We hypothesize that post-laminectomy patients who were administered intraoperative ketamine and methadone will have improved postoperative pain scores than those receiving intraoperative ketamine or methadone alone. As explained above, methadone, an opioid agonist weak NMDA antagonist, and ketamine, a strong NMDA antagonist, are individually effective for pain control via separate molecular pathways. We believe that the treatment of pain by two separate pathways will cause a synergistic effect greater than the pain control produced by either medication alone. Our secondary hypothesis is that following lumbar laminectomy, patients given intraoperative ketamine and methadone will require less opiates postoperatively than those receiving ketamine or methadone only.

SUMMARY OF STUDY DESIGN

The proposed study is a randomized, double-blinded, placebo-controlled evaluation of intraoperative ketamine and methadone on postoperative pain and opioid requirements for chronic pain patients undergoing lumbar laminectomy.

Three intervention groups will include:

1. Ketamine group: A bolus of intravenous (IV) ketamine during induction (0.5mg/kg), and an IV infusion of ketamine intraoperatively (5 mcg/kg/min)

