Ketamine + Methadone	Preinduction: 0.2 mg/kg methadone IV bolus Induction: ketamine 0.5 mg/kg IV bolus Infusion: ketamine 5 mcg/kg/min IV

III. Preoperative Evaluation (on the day of surgery):

- In the preoperative holding area, patients will provide a detailed medical history, including demographic information (e.g., age, weight, height, ethnic origin, smoking history, anesthetic complications such as postoperative nausea and vomiting, baseline VRS pain scores, and current pain medication regimen. An anesthesiologist will perform

the physical exam and written informed consent will be obtained by one of the investigators.

b. Enrollment numbers: A total of 114 patients, aged 18-80 years, American Society of Anesthesiology (ASA) physical status I – III undergoing lumbar laminectomy will be randomly assigned to one of three study groups:

Group I	Ketamine (n = 38)
Group II	Methadone (n = 38)
Group III	Ketamine & Methadone (n= 38)

IV. Intraoperative period:

- a. Premedication: Midazolam 20 ug/kg IV for anxiolysis, amnesia, and sedation synergism.
- b. Standard monitors: automatic blood pressure cuff, non-invasive blood pressure three-lead electrocardiogram, capnograph, pulse oximeter, urinary temperature monitor and bispectral index (BIS) monitor will be used. Patient will be pre-oxygenated with a simple face mask at 6 L/min for at least 2 minutes.
- c. Anesthesia induction technique: Fentanyl 50-100 mcg IV, propofol 1.5-3 mg/kg IV with lidocaine 1-1.5 mg/kg IV will be given for induction. Choice of muscle relaxant for intubation will be left up to the discretion of the anesthesiologist. Both histamine release from succinylcholine and the mild vagal blockade of rocuronium are negligible and are not known to interfere with pain control.
- d. Normothermia will be maintained with forced-air warming and IV fluid warmers.
- e. Administration of study medication will occur as follows:

Group	Dosing (IBW used for mg/kg dosing)
I – Ketamine	Preinduction: Sham (0.9% normal saline, volume calculated to match methadone dose) Induction: 0.5 mg/kg IV bolus Infusion: 5 mcg/kg/min IV
II – Methadone	Preinduction: 0.2 mg/kg IV bolus Induction: Sham (0.9% normal saline, volume calculated to match ketamine induction dose) Infusion: Sham (0.9% normal saline at infusion rate calculated and adjusted for weight to match ketamine bolus-infusion rate)

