- I. Preoperative demographics: age, weight, BMI, gender, ASA status, race, preoperative medications including beta-blockers and Lidoderm patches, prior back surgery, prior pain procedures, past medical/surgical history, social history (smoking, drinking, illicit drug use) allergies, history of postoperative nausea and vomiting, history of motion sickness and short-form 12 (SF-12) score after completing the survey. Name, phone number, e-mail address, and medical record number will be collected and stored in a secured separate file to prevent bias and inadvertent unblinding. Only the study coordinator will have access to this file and the patient will be referred to solely by subject number.
- II. Preoperative data: baseline VRS pain score, vital signs (blood pressure, heart rate, temperature, respiratory rate, oxygen saturation via pulse oximetry), 12-lead EKG interpretation, duration of pain, any abnormal lab results, additional surgical procedures (e.g., fusion, discectomy), and number of levels.
- III. Intraoperative data:
 - Vital signs (including blood pressure, heart rate), BIS values, every 5 – 10 minute intervals
 - dosages of all medications given (anesthetics, analgesics, local anesthetics, rescue medications, adjuncts such as decadron, end-tidal desflurane concentration, rate of propofol infusion), IV fluids, blood products, colloids, blood loss, urine output
 - Duration of surgery (from skin incision to closure), duration of anesthesia (from IV induction until anesthetic drug discontinuation)

IV. Postoperative data:

- Time on arrival to PACU, departure, and total length of stay
- VRS pain score and nausea on arrival to the PACU, vital signs, opiate and antiemetic requirements in the PACU
- PACU complications such as respiration depression (respiratory rate < 8, need for naloxone, or respiratory arrest), hypoxemia or desaturation ($\text{SpO}_2 < 90\%$ or need of supplemental oxygen to maintain $\text{SpO}_2 > 95\%$), hypotension, cardiac arrhythmias, myocardial infarction, nausea and vomiting, respiratory distress.
- Total opioid, adjuvant (e.g., anticonvulsants, antispasmodics, SSRI's) and antiemetic consumption at 24, 48, and 72 hours following surgery. If patients are discharged from the hospital prior to 72 hours, a telephone interview will be conducted to determine opioid/adjuvant consumption at home.

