Test significance level, α	0.050	0.025	0.050	0.025
1 or 2 sided test?	2	2	2	2
Group 1 mean, μ_1				
Group 2 mean, μ_2				
Difference in means, $\mu_1 - \mu_2$	2.000	2.000	1.800	1.800
Common standard deviation, σ	2.000	2.000	2.000	2.000
Effect size, $\delta = \mu_1 - \mu_2 / \sigma$	1.000	1.000	0.900	0.900
Power (%)	80	80	80	80
n per group	17	21	21	25

Based on the power analysis, a sample size of 38 patients for each group will sufficiently allow us to detect at least a 30% reduction in postoperative opioid consumption and VAS pain scores with 80% power using a two sample t-test, significance level of 0.05 (two-sided). Total sample size will be 114.

ANOVA will be used to compare the continuous variables among the three treatment groups, and when significant differences are determined, a Newman-Keuls multiple-comparison test will be used to determine intergroup differences. Continuous data not normally distributed are analyzed by Kruskal-Wallis test, and when a significant difference is found, a Mann-Whitney U test is used for post-hoc comparisons between the intergroups. Chi-squared test (or Fisher's exact test) is used to analyze the categorical variables such as side effects and sex distribution.

INCLUSION & EXCLUSION CRITERIA

I. Inclusion criteria:

- 18 – 80 years old of either gender, scheduled for elective lumbar laminectomy

II. Exclusion criteria:

- ASA IV and above
- Intolerance, allergy, or contraindication to use of any medications used in this study
- Significant coronary artery disease (abnormal stress test, myocardial infarction within the last 3 months)
- Increased intraocular pressure (e.g., untreated glaucoma)
- Uncontrolled hypertension (BP > 140/90)
- Sleep apnea AND currently on continuous positive airway pressure (CPAP)
- Increased intracranial pressure or clinical signs thereof
- History of intracranial surgery, stroke, or brain aneurysm
- Cardiac arrhythmias particularly prolonged QT syndrome
- Drugs known to cause prolonged QT: class IA antiarrhythmics (quinidine, procainamide, dysopyramide), class III antiarrhythmics (sotalol, dofetilide, ibutilide, amiodarone), haloperidol, thioridazine, arsenic trioxide, HIV protease inhibitors, tricyclic antidepressants
- Individuals with significant psychological disorders including: schizophrenia, mania, bipolar disorder or psychosis
- Pregnant or lactating women
- Emergent laminectomy
- Those already receiving ketamine or methadone prior to surgery

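### Continuous outcomes are compared without adjustment although prognostic baselines are already collected, and no single primary outcome and time point is named

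*Combined protocol and SAP*

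**What the plan says.** **Analysis.** Data Analysis states that "ANOVA will be used to compare the continuous variables among the three treatment groups", followed by Newman-Keuls if significant. For non-normal data, Kruskal-Wallis comes first and then "a Mann-Whitney U test is used for post-hoc comparisons between the intergroups". No covariate, stratification factor or repeated-measures model is mentioned.

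**Baselines collected.** Methods III (Preoperative Evaluation) records "baseline VRS pain scores, and current pain medication regimen". Patient Data Collection II records "additional surgical procedures (e.g., fusion, discectomy), and number of levels".

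**Outcomes.** Objective 1 asks whether the combination "reduces postoperative pain scores and opioid consumption more than single NMDA antagonism with ketamine or methadone alone". In Background & Significance, the leading hypothesis is that combination patients "will have improved postoperative pain scores than those receiving intraoperative ketamine or methadone alone". It then continues: "Our secondary hypothesis is that following lumbar laminectomy, patients given intraoperative ketamine and methadone will require less opiates postoperatively". Data Analysis bases the sample size on opioid consumption, adds a pain calculation, and concludes that 38 per arm serves both.

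**Times.** Summary of Study Design schedules pain and opioid use on days one to three and at six weeks. Patient Data Collection IV specifies "antiemetic consumption at 24, 48, and 72 hours following surgery" (the same item covers opioids). With the PACU measurements there are up to six pain and five opioid assessments. Neither the hypotheses nor the power calculation names one of them.

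**The concern.** Baseline pain, prior opioid use and extent of surgery plausibly predict postoperative pain and opioid use. Background & Significance itself notes that baseline opioid requirements can be raised and often increase after surgery. Leaving these variables out puts explainable variation into the error term and makes no correction for chance imbalance between arms of 38.

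The second issue is which result decides the trial. The outcome ranked second is the one the sample size starts from, and no time point is fixed. The protocol expects ketamine's benefit mainly in the first 24 hours and methadone's relief to last up to 48 hours, so results may well differ by time. The conclusion could then depend on which measurement is emphasised once the data are known. It is also not stated formally whether the combination must beat both single drugs.

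**Working it through.** **1. Plan's own figure.** Opioid table, last column: difference 15 mg, SD 23, two-sided 0.05. Effect size 15/23 = 0.652. A two-sample t-test with 38 per arm has power 0.801, so the stated 38 reproduces.

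**2. Adjustment, before the gate.** Residual SD = 23 × √(1 − r²), where r is the multiple correlation of the covariates with the outcome. The documents give no value, so 0.2–0.6 is an assumption.

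| r | residual SD | t-test power |
|---|---|---|
| 0 | 23.00 | 0.801 |
| 0.2 | 22.54 | 0.817 |
| 0.4 | 21.08 | 0.865 |
| 0.6 | 18.40 | 0.939 |

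**3. With the planned gate.** The plan makes pairwise tests only after a significant three-group test. I simulated 3 × 38 with both single-drug arms 15 mg above the combination, an F test at 0.05, then pairwise t-tests. Power per contrast is about 0.76 unadjusted (0.75 with Newman-Keuls), and about 0.78, 0.83 and 0.93 at r = 0.2, 0.4 and 0.6. Estimating four coefficients costs a little. With all four estimated, I get about 0.76, 0.83 and 0.92.

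**4. Cost if the covariates predict nothing.** Residual degrees of freedom fall from 111 to 107. Ungated power falls from 0.801 to 0.786, a loss of about 0.015.

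**5. Rank scale.** Data Analysis expects skew. Assume log-normal data with mean 67 and SD 38 (the cited ketamine figures) and a 30% reduction. Mann-Whitney power is 0.80 alone and 0.76 after a significant Kruskal-Wallis test. A rank model with four covariates, ungated, gives 0.81, 0.86 and 0.93 at r = 0.2, 0.4 and 0.6. The like-for-like comparison is with 0.80.

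**6. Several times, each tested at 0.05.** For the four pain times in Summary of Study Design, if independent: 1 − 0.95⁴ = 0.185. With a correlation of 0.7 between times, simulation gives about 0.13. The range is therefore 13–19%.

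**7. Both contrasts required.** At 15 mg and SD 23 for each contrast, power is about 0.69 (about 0.67 with Newman-Keuls).

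**8. Pain, SD 2.0, 38 per arm, t-test per contrast.** Against the cited ketamine mean: 0.30 × 5.4 = 1.62, the plan's 1.6 points. Effect size 1.6/2.0 = 0.80, power 0.93. Against the cited methadone mean: 0.30 × 2.8 = 0.84 points. Effect size 0.84/2.0 = 0.42, power 0.44.

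**9. Does the gate control pairwise error?** Simulated with the F gate and unadjusted pairwise t-tests, the chance of any false pairwise claim is 0.049 when all arms are equal. With one arm far away, the remaining null pair is rejected 0.050 of the time.

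**The case against.** *Omitting covariates is not an error.* This stands. A reader might infer that the unadjusted tests are biased or invalid. Under randomisation they are neither, and at r = 0.2 the gain roughly offsets the cost of estimating the coefficients.

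*The plan implies a primary outcome and sizes it.* Partly right. Pain is ranked first, and Data Analysis sizes pain as well as opioid use. Sizing on the more demanding outcome is compatible with pain being primary, so it would be wrong to say the trial was sized on opioid use alone. But no outcome is labelled primary and no time is given. The pain table has columns at alpha 0.025, but no multiplicity rule is attached and the concluding sentence uses 0.05.

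*The success rule is implied.* Also partly right. Background & Significance predicts an effect exceeding that of each drug by itself, which points to superiority over both. It is not written as a decision rule, and the 80% power was not computed for it.

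*The 0.05 should be divided between the two contrasts.* A reader might infer this, but with three groups the omnibus gate already holds pairwise error at about 0.05 for one outcome at one time. Requiring both contrasts is stricter still.

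*The false-positive risk is far higher across all eleven pain and opioid assessments.* Simulation gives up to about 43%. That is a ceiling under independence, which repeated measurements on the same patients do not meet. The documents also nowhere say that any one of the eleven would count as success.

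**Conclusion.** The point holds as a matter of efficiency and prespecification, not validity. Adjustment would raise gated power per opioid contrast from about 0.76 to about 0.83 at r = 0.4 and 0.93 at r = 0.6. The gain is close to nil at 0.2, and there is a loss of about 0.015 if the covariates carry no information. These figures rest on the assumed correlations and on taking the plan's 15 mg and SD 23 as given.

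The missing primary outcome and time point do not depend on any assumption. The 13–19% does: it assumes that each of the four pain times would be tested at 0.05 and any one of them counted.

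The stated 80% power does not carry over to a requirement that the combination beat both drugs on opioid use (about 0.69), nor to a 30% pain reduction against methadone (0.44). It is met for pain at 1.6 points (0.93 per contrast). A reader might conclude that the trial must be enlarged. The finding does not require that: the need is to state what 38 per arm can show.

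**What to change.** Before unblinding:

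1. **Main analysis.** Use ANCOVA, keeping the three-group omnibus test before the pairwise contrasts. Adjust for baseline VRS pain, number of levels, fusion (yes/no) and preoperative opioid use (yes/no, from the recorded regimen). Analyse opioid use on the rank scale, fixed now so that neither scale nor covariate form is chosen from the data. Keep the planned ANOVA and rank tests as supportive.
2. **Primary outcome.** Name one outcome at one time point, reconcile the hypotheses in Background & Significance with the sample-size basis in Data Analysis, and label all other outcomes and times secondary.
3. **Success rule and power.** State that success means the combination beats ketamine alone and methadone alone. Restate power at 38 per arm: about 0.69 for both opioid contrasts at 15 mg and SD 23 (about 0.67 with Newman-Keuls); for pain, 0.93 per contrast at 1.6 points and 0.44 at 0.84 points. No division of 0.05 between the contrasts is needed while the omnibus gate is kept.

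The cost is plan wording and some programming on data already collected, plus four of 111 residual degrees of freedom. The less comfortable cost is that the restated power is below 80% for some claims. No added enrolment is proposed.

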- VRS pain scores, vital signs and medication side effects (e.g., ketamine-induced hallucinations) at 24, 48, and 72 hours following surgery; time to return of daily activities (oral diet, return of bowel function, ambulation, showering) in days, any complications such as cardiac arrhythmias, global evaluation of anesthesia experience with 0 = worst, 10 = best
- Length of hospital stay

V. 6 week post-surgical assessment data:

- VRS pain score, opioid/adjuvant consumption, medication side effects (e.g., hallucinations, constipation, nausea and vomiting), SF-12 score.

Note: all opioid consumption will be converted to morphine equivalents for data analysis and presentation.

DATA ANALYSIS

Sample size estimates were based on the test for inequality of opioid consumption among the methadone, ketamine, and ketamine + methadone groups. We expect to observe at least a 30% decrease in opiate consumption between ketamine + methadone group and methadone or ketamine. Prior studies demonstrated that the postoperative opioid consumption and its standard deviation for methadone and ketamine are quite similar (10, 21). Mean opioid consumption was approximately 67 mg \pm 38 mg (SD) for Menigaux's et al. ketamine group and median 63 mg (interquartile range, 27-86.1), which gives an estimated SD of 23. The expected group mean difference would be 18.9 for an approximate 30% decrease in opioid requirements. However, we would like to be more conservative in our study since the aforementioned study populations were most likely skewed. For a two-tailed hypothesis with alpha 0.05, we would need at least 38 subjects per group to achieve a power of 0.8 to detect a 30% reduction in opioid consumption.

Two group t-test of equal means (equal n's)

	1	2	3	4
Test significance level, α	0.050	0.050	0.050	0.050
1 or 2 sided test?	2	2	2	2
Group 1 mean, μ_1				
Group 2 mean, μ_2				
Difference in means, $\mu_1 - \mu_2$	18.900	20.000	17.000	15.000
Common standard deviation, σ	23.000	23.000	23.000	23.000
Effect size, $\delta = \mu_1 - \mu_2 / \sigma$	0.822	0.870	0.739	0.652
Power (%)	80	80	80	80
n per group	25	22	30	38

Similarly for VAS pain scores, previous studies found average scores to range from 2.8 ± 2.0 for methadone group and 5.4 ± 2.0 for the ketamine study (7, 10). With alpha 0.05, power 0.8 and mean difference of 1.6, each group needs at least 17 subjects to observe a 30% reduction in VAS pain scores.

Two group t-test of equal means (equal n's)

	1	2	3	4

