Ketamine has been approved by the FDA and is used widely in the U.S. for anesthetic and pain management arenas. It has been well-studied in both animal model and human subjects. Of note, the side effect likelihood listed below for ketamine represent the induction dose side effect profile. Ketamine side effects are dose-dependent, and subanesthetic ketamine doses such as that used for analgesia are mild and less likely to occur (6). For instance, CNS side effects (dizziness, dysphoria, confusion, drowsiness, hallucinations) analyzed from pooled data did not reveal any significant differences: 18% in postoperative ketamine plus morphine vs. 15% in morphine PCA groups ($P = 0.31$; RR, 1.27; 95% CI, 0.80, 2.01) (23). Incidence of CNS side effects for ketamine patients were 18%, 10%, 9%, and 0.7% with IV PCA, IV infusion, IV single dose, and epidural groups. The psychogenic effects (dysphoria, confusion, hallucinations) will be mitigated by midazolam premedication. Patients with significant coronary artery disease (abnormal stress test, recent angina, MI within the last 3 months) will be excluded due to increased cardiac demand (from increased blood pressure, tachycardia). Patients with increased intracranial pressure (ICP) and untreated high intraocular pressure (IOP) will also be excluded from the study.

	Very Likely (>25%)	Likely (10-25%)	Less Likely (1-9%)	Rare (<1%)
Ketamine	
 • Blurred vision • Confusion 	
 • Increased or decreased blood pressure or heart rate • Mental or mood instability • Psychotic thoughts • Hallucinations 	
 • Vomiting • Nausea • Nightmares • Drowsiness 	
 • Difficulty talking • Irregular heart rhythms • Muscle tightness • Redness, or swelling at the injection site • Allergic reactions (rash, itching, difficulty breathing)
Methadone	
 • Drowsiness • Dizziness 	
 • Low Blood Pressure 	
 • Slower or faster heart 	
 • Increased intracranial

		
 • Constipation • Nausea • Slowed respiratory rate 	
 • Confusion • Orthostatic hypotension • Dry mouth • Biliary tract spasm • Blurred vision • Stomach cramps • Anxiety 	
 • rate 	
 • pressure

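### Side effects get a chi-squared or Fisher test with no pairwise comparison or effect estimate, so the categorical part of Objective 2 (combination versus each drug alone) is not answered

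*Combined protocol and SAP*

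**What the plan says.** STUDY OBJECTIVES, item 2, reads: "To compare the side effects and hospital course between post-laminectomy patients receiving intraoperative ketamine + methadone vs. ketamine or methadone alone". That is two comparisons, each with the combination on one side.

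The last paragraph of DATA ANALYSIS sets the tests by type of variable:

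- Continuous, normally distributed: ANOVA, and if significant, "a Newman-Keuls multiple-comparison test will be used to determine intergroup differences".
- Continuous, not normally distributed: Kruskal-Wallis, and if significant, "a Mann-Whitney U test is used for post-hoc comparisons between the intergroups".
- Categorical: "Chi-squared test (or Fisher's exact test) is used to analyze the categorical variables such as side effects and sex distribution". Nothing follows.

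For side effects the plan names no pairwise step, effect estimate, confidence interval or multiplicity rule. It does not say whether the test is run on all three arms at once or on pairs.

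The sample size in the same section is argued from opioid consumption ("we would need at least 38 subjects per group to achieve a power of 0.8") and from pain scores. No power statement is made for side effects.

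**The concern.** Side effects are the first thing Objective 2 names, yet they are the one class of outcome without a step that isolates the combination. A single p-value across three arms says that some arms differ, not which. It cannot tell a reader whether adding methadone to ketamine, or ketamine to methadone, raises the rate of a given side effect, or by how much.

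The background section says that the combined effects of the two drugs are largely unknown, so the size of any added harm is what readers will want. If contrasts are chosen only after the data are seen, the choice can follow the results. If the three-group test is not significant, the lack of an interval makes it easy to take the result as reassurance. POTENTIAL RISKS already cites a non-significant comparison of CNS effects (18% versus 15%, P = 0.31) in support of low risk, although its interval for the risk ratio, 0.80 to 2.01, includes a doubling.

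**Working it through.** **Inputs from the protocol.** 38 per arm, 114 in total; two-sided alpha 0.05; power 0.80 for opioid use and pain only. Rates by arm are assumptions. The protocol gives side-effect bands for each drug but none for the combination, and says that the ketamine bands describe induction doses. No dropout allowance is stated, so the full 38 per arm is used.

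**1. The plan's own figure.** Difference 15, SD 23:

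n = 2(1.96 + 0.842)² × 23² / 15² = 36.9, so 37 by the normal approximation. The exact t-test calculation gives 37.9, so 38. The stated 38 per group is reproduced. It is a figure for opioid consumption and says nothing about event rates.

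**2. What a three-group test can show.** Pearson's statistic, Σ(O − E)²/E on 2 df, is unchanged when the arm labels are swapped. Rates of 15/15/30% (ketamine/methadone/combination, combination worst) and 30/15/15% (ketamine alone worst) therefore have the same chance of significance and give the same kind of p-value. Only a pairwise step separates them.

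**3. Power of the three-group test, 38 per arm** (simulated trials, Pearson chi-squared at 0.05):

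| Ketamine / methadone / combination | Power |
|---|---|
| 10 / 10 / 20% | 23% |
| 15 / 15 / 30% | 37% |
| 25 / 1 / 25% | 96% |

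**4. Power of one planned contrast.**

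Power = Φ{[|p₁ − p₂| − z√(2p̄(1 − p̄)/n)] / √[(p₁(1 − p₁) + p₂(1 − p₂))/n]}

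- 10% versus 20%: p̄ = 0.15; (0.10 − 1.96 × 0.0819)/0.0811 = −0.75; power 23%.
- 15% versus 30%: p̄ = 0.225; (0.15 − 1.96 × 0.0958)/0.0942 = −0.40; power 34%.

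At alpha 0.025 (Bonferroni for two contrasts, the stricter threshold within Holm) these become 15% and 25%. For 80% power at 0.05 they would need 199 and 121 per arm.

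**5. Precision.** The 95% CI half-width for a risk difference at 10% versus 20% is 1.96 × √[(0.1 × 0.9 + 0.2 × 0.8)/38] = 0.159, about ±16 points. With no events in 38 patients, the exact two-sided upper limit is 1 − 0.025^(1/38) = 9.3%.

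**The case against.** The strongest reply is that this is under-specification rather than a wrong test. The sentence does not say that the test spans three arms; pairwise 2×2 Fisher tests would fit the wording. That stands, and the point is worded accordingly. It does not remove the gap: the two contrasts in Objective 2 are not named and no effect estimate is planned on either reading.

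It is also true that low power comes from the sample size, which was set for other outcomes, and that naming contrasts does not cure it (23% either way at 10% versus 20%). The gain from the change is a direct answer with visible uncertainty, not power. Nothing in the protocol plans a claim of equal safety, so that misreading is a risk to guard against, not a fault in the text. Continuous hospital-course items, such as length of stay, already have follow-up tests and are outside this point.

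A reader might infer two stronger things, neither of which the documents support.

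- *That a significant three-group result will usually reflect ketamine versus methadone.* When one drug causes the effect and the combination shares its rate, the combination differs from the other drug about as often. In simulations at 25/1/25%, 18/1/18% and 5/25/25%, at least one combination contrast was significant in 92 to 98% of significant results. Even with the combination between the two drugs (35/5/20%, 30/10/20%, 5/35/20%), ketamine versus methadone was the only significant pair in just 16 to 30%. Assuming almost no CNS effects on methadone also conflicts with POTENTIAL RISKS, which counts drowsiness and dizziness as CNS effects and lists both above 25% for methadone. With that section's 18% for ketamine plus morphine and 15% for morphine alone as a guide, 18/15/18% makes the three-group test significant in only 6% of trials, close to its false-positive rate.
- *That a non-significant result is uninformative.* It carries information against very large differences: 25/1/25% would be detected in 96% of trials. It is weak only against moderate ones.

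**Conclusion.** The point holds for the categorical side effects in Objective 2. The plan names a test but neither of the comparisons that the objective asks for, and gives no estimate of their size. If the test is run across three arms, it does not show which arms differ.

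Non-significance would be weak evidence of similar safety: a doubling from 10% or 15% in both single-drug arms would be missed in about 77% or 63% of trials. Those figures rest on assumed rates and on all 38 patients per arm being analysed. The gap in the analysis does not depend on the rates; it follows from setting Objective 2 beside the analysis paragraph.

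**What to change.** In DATA ANALYSIS, replace the side-effect part of the categorical sentence with two pre-specified contrasts: combination minus ketamine, and combination minus methadone.

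- For each named side effect, count any occurrence per patient and report each contrast as a risk difference with a 95% CI. Add Fisher's exact test per contrast if a p-value is wanted.
- Either apply Holm over the two contrasts or label the side-effect analysis descriptive.
- State that the trial is not powered for side effects and that a non-significant contrast will not be reported as equal safety.

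The cost is a few sentences and some table work, with no added patients or data. The small downside is that the report will show wide intervals; that uncertainty exists under the current plan too, but is not displayed.
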